7.2. Appendix 2 Changes to Protocol-Planned Analyses

In the section 6.4.1.2, α_4 was added in the following sentence: The VE against the primary endpoint will be tested using the significance level α' (α_1 or α_2 or α_3 or α_4), as defined in Section 6.3.2.

The following exploratory endpoint was added:

- First occurrence of predefined clinically relevant disease associated with RT-PCR-confirmed RSV-mediated ARI and LRTD

This was already a secondary endpoint for the end of study analysis.

The following exploratory analysis was added:

- First occurrence of RT-PCR-confirmed RSV-mediated LRTD will be calculated, based on the four quartiles of the EQ visual analogue scale collected at baseline for the PPE participants

7.3. Appendix 3 Demographics and Baseline Characteristics

The following demographic and baseline characteristics will be summarized.

Table 16 presents a list of the demographic variables that will be summarized by vaccine regimen and overall, for the for the full analysis set and by vaccine regimen for safety subset, PPE, PPI and for participants with an RT-PCR confirmed RSV-mediated ARI as well based on the risk level of the participant. Demographics will also be summarized by region using the FAS analysis set. Demographics may also be summarized by age category.

Table 16: Demographic Variables

Continuous Variables:	Summary Type
Age (years)	Descriptive statistics (N, median , mean, standard deviation, minimum and maximum).
Weight (kg)	
Height (cm)	
Body Mass Index (BMI) (kg/m ²)	
Categorical Variables	Frequency distribution with the number and percentage of participants in each category.
Age categories (60-64 years, 65-74 years, 75-84 years, ≥85 years)	
Sex (male, female, intersex)	
Race ^a (American Indian or Alaska Native, Asian, Black or African American, Native Hawaiian or other Pacific Islander, White, Multiple)	
Ethnicity (Hispanic or Latino, not Hispanic or Latino)	
Risk Level (CDC definition), as collected	
COPD (for increased risk)	
CHF (for increased risk)	
Asthma (for increased risk)	
other chronic heart disease (for increased risk)	
other chronic lung disease (for increased risk)	
Risk Level (CDC definition + CKD + Diabetes)	
BMI (underweight <18.5 kg/m ² , normal or healthy weight 18.5-<25 kg/m ² , overweight 25-<30 kg/m ² , obese ≥30 kg/m ²)	
Region (Northern America, Europe , South America, Asia, Australia/New Zealand, Africa)	
Country	
Smoking status	
HIV status	
COVID-19 vaccination status at baseline . Participants receiving at least one dose of: 
 • AstraZeneca COVID-19 vaccine • Janssen Covid-19 vaccine • Moderna COVID-19 vaccine • Pfizer COVID-19 vaccine • Other COVID-19 vaccine • No COVID-19 vaccination — (participants might be counted in multiple categories)	

^a If multiple race categories are indicated, the Race is recorded as 'Multiple'

7.4. Appendix 4 Protocol Deviations

Major protocol deviations will be summarized per year, per vaccine group, increased level subgroup and overall.

In general, a list of major protocol deviations may have the potential to impact participants' rights, safety or well-being, or the integrity and/or result of the clinical study. Participants with major protocol deviations will be identified prior to database lock and the participants with major protocol deviations will be summarized by category. In addition, minor and major protocol deviations related to COVID-19 will be tabulated.

7.5. Appendix 5 Prior and Concomitant Medications

The analysis of concomitant therapies will be done using the WHO drug coded terms. Concomitant medications associated with SAE will be collected through the study, as well as concomitant medications associated with ARI episodes and with complications of ARI will be recorded for all participants during all ARI episodes for the duration of the two study years.

Based on their start and stop date, concomitant therapies will be reported in each applicable phase.

If a concomitant therapy record misses components of its start and/or stop dates (time, day and/or month and/or year):

- In case of partial start or stop dates, the concomitant therapy records will be allocated to periods using the available partial information, without imputations. If, for example, only month and year are available, these will be compared to the month and the year of the periods, and the concomitant therapy record will be allocated to the period(s) where these date parts match. This rule may lead to assignment to multiple periods. The same rule applies for identifying whether a concomitant therapy was administered during 8 days following a vaccination. If for example, the vaccination was administered on the 30 December 2017 and the concomitant therapy start date is January 2018, then the concomitant therapy will be assumed to have started within 8 days of the vaccination.
- In case of a completely missing start date, the concomitant therapy will be considered as having started before the study.
- In case of a completely missing end date, the concomitant therapy will be considered as ongoing at the end of the study.

For the use of analgesics/antipyretics (definition below) which are taken on the day of vaccination, an exception is made in case the time is before vaccination. In this case, the concomitant medication is also allocated to the post-dose period.

There will be special attention to:

- analgesics/antipyretics such as acetaminophen, non-steroidal anti-inflammatory drugs (NSAIDs) and aspirin, that started being administered during 8 days following the vaccination (00:00 of day of vaccination + 7 days), based on the safety subset. The following codes will be used for this: N02A (OPIOIDS) and N02B (OTHER ANALGESICS AND ANTIPYRETICS), M01A (ANTIINFLAMMATORY AND ANTIRHEUMATIC PRODUCTS, NON-STEROIDS) and M01B (ANTIINFLAMMATORY/ANTIRHEUMATIC AGENTS IN COMBINATION) ([ATC/DD Index](#)). The classes will be added in a footnote in all related tables and listings
- all concomitant medications for the safety subset
- concomitant medications related to SAEs, based on the FAS
- emerging therapeutic interventions of interest associated with RT-PCR confirmed RSV-mediated ARI episodes and with complications of RT-PCR confirmed RSV-mediated ARI based on the PPE set.

- new concomitant medications that are not part of the therapeutic interventions of interest associated with RT-PCR confirmed RSV-mediated ARI episodes and with complications of RT-PCR confirmed RSV-mediated ARI based on the PPE set.

New concomitant medications and emerging therapeutic interventions are defined as medications not available at baseline or medication with an increased dosage, compared to baseline and are indicated by the principal investigator.

7.6. Appendix 6 Guidance for Industry: Toxicity Grading Scale for Healthy Adult and Adolescent Volunteers Enrolled in Preventive Vaccine Clinical Trials

Adapted from the FDA Guidance document “Toxicity Grading Scale for Healthy Adult and Adolescent Volunteers Enrolled in Preventive Vaccine Clinical Trials” (September 2007)

Vital Signs *	Mild (Grade 1)	Moderate (Grade 2)	Severe (Grade 3)	Potentially Life-threatening (Grade 4)
Fever (°C) ** (°F)**	38.0-38.4 100.4-101.1	38.5-38.9 101.2-102.0	39.0-40.0 102.1-104.0	>40 >104.0
Tachycardia - beats per minute	101-115	116-130	>130	Hospitalization for arrhythmia [#]
Bradycardia - beats per minute***	50-54	45-49	<45	Hospitalization for arrhythmia [#]
Hypertension (systolic) - mm Hg	141-150	151-160 [#]	>160 [#]	Hospitalization for malignant hypertension [#]
Hypertension (diastolic) - mm Hg	91-95	96-100	>100	Hospitalization for malignant hypertension [#]
Hypotension (systolic) - mm Hg	85-89	80-84	<80	Hospitalization for hypotensive shock [#]
Respiratory Rate - breaths per minute	17-20	21-25	>25	Intubation

* Participant should be at rest for all vital sign measurements.

** For oral temperature: no recent hot or cold beverages or smoking.

*** When resting heart rate is between 60 - 100 beats per minute. Use clinical judgment when characterizing bradycardia among some healthy participant populations, for example, conditioned athletes.

[#] Revised by the sponsor.

For the vital signs' analysis in Section 6.6.5 only values will be used to assign abnormalities, no clinical interpretations will be used. Therefore, grade 3 and 4 will be combined because grade 4 always requires clinical interpretation.

7.7. Appendix 7 Respiratory Viruses and Bacteria Used to Define Coinfections

The following respiratory viruses will be evaluated by the BioFire® Filmarray RP2.1-EZ on the nasal swab:

- Adenovirus
- Coronavirus 229E
- Coronavirus HKU1
- Coronavirus NL63
- Coronavirus OC43
- Coronavirus SARS-CoV-2
- Human Metapneumovirus
- Rhinovirus/Enterovirus
- Influenza A, including subtypes H1, H3 and H1-2009
- Influenza B
- Parainfluenza Virus
- Respiratory Syncytial Virus

The following respiratory bacteria will be evaluated by the BioFire® Filmarray RP2.1-EZ on the nasal swab:

- Bordetella parapertussis
- Bordetella pertussis
- Chlamydia pneumoniae
- Mycoplasma pneumoniae

The following based on the BioFire Filmarray PN assay from the sputum sample:

- Adenovirus
- Coronavirus
- Human Metapneumovirus
- Human Rhinovirus/Enterovirus
- Influenza A
- Influenza B
- Parainfluenza Virus
- Respiratory Syncytial Virus

The following respiratory bacteria will be evaluated by the BioFire Filmarray PN assay from the sputum sample:

- Acinetobacter calcoaceticus-baumannii complex
- Enterobacter cloacae complex
- Escherichia coli
- Haemophilus influenzae
- Klebsiella aerogenes
- Klebsiella oxytoca

- *Klebsiella pneumoniae* group
- *Moraxella catarrhalis*
- *Proteus* spp.
- *Pseudomonas aeruginosa*
- *Serratia marcescens*
- *Staphylococcus aureus*
- *Streptococcus agalactiae*
- *Streptococcus pneumoniae*
- *Streptococcus pyogenes*
- *Chlamydia pneumoniae*
- *Legionella pneumophila*
- *Mycoplasma pneumoniae*

For samples collected in China, the following respiratory viruses will be evaluated by the Cepheid GeneXpert on the nasal swab:

- Influenza A
- Influenza B
- Respiratory Syncytial Virus

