9. STATISTICAL CONSIDERATIONS

Statistical analysis will be done by the sponsor or under the authority of the sponsor. A general description of the statistical methods to be used to analyze the efficacy, safety and immunogenicity data is outlined below. Specific details will be provided in the Statistical Analysis Plan. This section focusses on the key statistical considerations for the Global cohort. Analyses for local cohort enrollment will be described separately, but local cohorts will also be included in the primary analysis and final analysis if their enrollment started prior to the database cut-off of the primary analysis or final analysis, respectively.

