- Confirmation of RSV infection by RT-PCR in nasal swabs is obtained at the site laboratory with the BioFire Filmarray RP2.1-EZ panel, which will be provided to all sites (both US and non-US, except China sites). Both the home swab and the site swab will be analyzed at the site. The confirmation of RSV infection from the nasal swab at central laboratory using BioFire will not be taken into account for the primary endpoint, unless in the unlikely event where at least one nasal swab from an ARI episode cannot be tested at the site (eg, in the setting of instrument malfunction or shortage of testing reagents at the site).
- Confirmation of RSV infection by RT-PCR in sputum samples (when collected) is obtained in the central laboratory with the Biofire Filmarray PN panel.
- For participants hospitalized with symptoms of an ARI, confirmation of RSV infection using a locally approved RT-PCR test obtained at the hospital laboratory can also be used. These results will be used in the primary analysis only if approved by an independent expert with expertise in diagnostic testing. The approval of the RT-PCR results by the expert will be based on the specifications of the test performed, the qualifications of the testing laboratory and the procedures followed in the laboratory.

For samples collected in China, a sample is considered RSV positive if:

- Confirmation of RSV infection by RT-PCR in nasal swabs is obtained at the site laboratory with the Cepheid GeneXpert Flu-RSV XPRESS, which will be provided to all China sites. Both the home swab and the site swab will be analyzed at the site. The confirmation of RSV infection from the nasal swab at central laboratory using Cepheid GeneXpert Flu-RSV XPRESS will not be taken into account for the primary endpoint, unless in the unlikely event where at least one nasal swab from an ARI episode cannot be tested at the site (eg, in the setting of instrument malfunction or shortage of testing reagents at the site).
- Confirmation of RSV infection by RT-PCR in sputum samples (when collected) is obtained in the central laboratory with the Biofire Filmarray PN panel.
- For participants hospitalized with symptoms of an ARI, confirmation of RSV infection using a locally approved RT-PCR test obtained at the hospital laboratory can also be used. These results will be used in the primary analysis only if approved by an independent expert with expertise in diagnostic testing. The approval of the RT-PCR results by the expert will

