For participants with an MPD impacting efficacy during the second year (during the second year follow up period), only the first year data are taken into account: for cases during the first year, the follow - up time is defined as the time between 14 days post-vaccination and occurrence of the first event . For non-cases, it is the time between 14 days post - vaccination and the day before Day 365 visit (or relative day 365, in case Day 365 not available but there are ARI surveillance questions available after the relative day 365). Thus, all participants will be included in the analysis according to their follow-up time.

Note: Occurrence is always referring to the start of the ARI as reported in the CRF (CESTDTC).

As **sensitivity analyses** the above Poisson model will be repeated similar to the primary analysis:

- based on the FAS (which also does not take into account the restriction on the onset [at least 14 days] and will count follow up from vaccination on Day 1 onwards).
- based on the PPE set but excluding coinfections with other respiratory viruses, based on the Biofire - Filmarray assay (Section 7.7) or the Cepheid GeneXpert (for swabs in China sites). This should be detected in one of the scheduled nasal or sputum samples linked to the respective ARI but should not necessarily be detected in the same sample as the one that resulted in RSV confirmation.
- based on the PPE set but excluding coinfections with other respiratory viruses or bacteria, based on the Biofire - Filmarray assay (Section 7.7) or the Cepheid GeneXpert (for swabs in China sites). This should be detected in one of the scheduled nasal or sputum samples linked to the respective ARI but should not necessarily be detected in the same sample as the one that resulted in RSV confirmation.
- based on the PPE set with age and increased risk status as collected (instead of as stratified) in case there are many discrepancies between as collected and as stratified.

- based on the PPE set but excluding RSV positive tests from local hospital assays of hospitalized participants.

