- First occurrence of pneumonia (radiological or X-ray confirmed, as assessed in the CRF diagnostic tests form or reported as a complication) associated with RT-PCR-confirmed RSV-mediated ARIs, RSV-mediated LRTD, influenza-mediated ARIs and hMPV-mediated ARIs
- First occurrence of emerging therapeutic interventions of interest associated with RT-PCR-confirmed RSV-mediated ARIs, RSV-mediated LRTD, influenza-mediated ARIs and hMPV-mediated ARIs. The following are considered emerging therapeutic interventions of interest (Section 7.10) :
 - New onset or increased dose (compared to baseline) of bronchodilator/nebulizer treatment

- New onset or increased dose (compared to baseline) of corticosteroid prescription
- New onset or increased dose (compared to baseline) of antibiotic prescription
- New onset or increased dose (compared to baseline) of antiviral prescription

Note: These will be taken from the concomitant medication pages of the eCRF. The concomitant medications listed in Section 7.10 are considered as therapeutic interventions of interest. The principal investigator will indicate whether there has been new onset of increase in dose compared to baseline in the CRF. Those associated with an ARI or complication of an ARI will be displayed.

- First occurrence of RT-PCR confirmed hMPV-mediated ARI
- First occurrence of RT-PCR-confirmed hMPV-mediated LRTD
- First occurrence of RT-PCR confirmed influenza-mediated ARI and influenza-mediated LRTD
- First occurrence of an RT-PCR-confirmed RSV LRTD assessed as at least mild, as at least moderate and as severe by the CEC during the considered year:
 - with onset at least 14 days after dosing of study vaccine and prior to study Day 365 (first year comparison)
 - with onset from the study Day 365 onwards (second year comparison)
 - with onset at least 14 days after dosing of study vaccine (whole study comparison)

Note: Occurrence is always referring to the time to the start of the ARI as reported in the CRF (CESTDTC). The start of the associated ARI will also be used for calculating the time to first occurrence of emerging therapeutic interventions, pneumonia, complications and hospitalizations.

- First occurrence of RT-PCR-confirmed, RSV-mediated LRTD during the second year and over the whole study (if the primary analysis is conducted before the end of the study):
 - with onset from the study Day 365 visit onwards (second year comparison)

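### In China, hMPV and non-influenza co-infections can be found only through sputum, yet China participants stay unrestricted in the hMPV endpoints and both co-infection sensitivity analyses

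*SAP*

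**What the plan says.** **Assays.** For China, SAP 6.3.1 says: "Confirmation of RSV infection by RT-PCR in nasal swabs is obtained at the site laboratory with the Cepheid GeneXpert Flu-RSV XPRESS". The central back-up for China swabs is the same assay: "The confirmation of RSV infection from the nasal swab at central laboratory using Cepheid GeneXpert Flu-RSV XPRESS will not be taken into account". The one exception is an episode with a swab that could not be tested on site. Sputum is handled as in other countries: "Confirmation of RSV infection by RT-PCR in sputum samples (when collected) is obtained in the central laboratory with the Biofire Filmarray PN panel".

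**Targets (SAP 7.7).**
- Swabs outside China (RP2.1-EZ): 12 viral entries, including hMPV, SARS-CoV-2 and rhinovirus/enterovirus, plus 4 bacteria.
- China swabs (GeneXpert): "For samples collected in China, the following respiratory viruses will be evaluated by the Cepheid GeneXpert on the nasal swab". That list has three entries, namely influenza A, influenza B and RSV; no bacteria.
- Sputum in all countries (PN panel): 8 viral entries, including hMPV, plus 18 bacteria.

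**Analyses.** SAP 6.3.3 repeats the primary model after removing RSV cases with another virus, and again after removing those with another virus or bacterium. Detection is by BioFire "or the Cepheid GeneXpert (for swabs in China sites"), in a scheduled nasal or sputum sample. SAP 6.5 includes "First occurrence of RT-PCR confirmed hMPV-mediated ARI" and the matching LRTD endpoint, both in the PPE set and both needing an hMPV-positive result.

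**Population.** Protocol section 9 says "local cohorts will also be included in the primary analysis and final analysis", provided their enrolment began before the relevant cut-off. SAP 5.1 likewise pools global and local cohorts for efficacy. Neither SAP 6.3.3 nor SAP 6.5 restricts or caveats China.

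**The concern.** A China participant whose hMPV episode yields no sputum is counted as a non-case and contributes follow-up time, although no test for hMPV was ever done. SAP 6.5.1 reports the proportion meeting each endpoint as well as efficacy, so this under-ascertainment shows directly in the reported hMPV proportions and event rates. It also carries into the endpoints built on hMPV episodes, such as complications and hospitalizations.

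The co-infection analyses check whether the primary result survives removal of cases of uncertain cause. For a China episode without sputum, the viral version can remove only influenza co-infections, and the viral-or-bacterial version removes no bacterial ones. An RSV case with rhinovirus on the swab is excluded elsewhere but kept in China. The case definition therefore varies by country, and the output does not say so.

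**Working it through.** The plan states no figure for this, so there is none to reproduce. The size has to be bounded under assumptions.

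**1. Which China cases are missed.** hMPV is not on the China swab list, either at the site or centrally. It is on the sputum panel ("The following based on the BioFire Filmarray PN assay from the sputum sample"). Protocol 8.1 takes sputum at ARI Day 3-5 from participants with a productive cough, when possible. The gap is therefore China episodes without a sputum result. The documents do not give that fraction.

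**2. Ceiling on the China share.** Protocol 4.1 allows up to about 4,200 participants in specific Asian countries/territories out of about 27,200: 4,200 / 27,200 = 15.4%. China is an unstated part of that. SAP 1.2 still carries 4,500 of 27,500, which is 16.4%; the amended protocol figure is used here.

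**3. Understatement of hMPV rates.** Let *s* be the China share of person-time and *q* the fraction of China hMPV cases found through sputum. Assume the same true incidence in China as elsewhere.

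Observed rate / true rate = (1 − *s*) + *s·q*, so the relative understatement is *s*(1 − *q*).

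| *s* | *q* = 0.5 | *q* = 0 |
|---|---|---|
| 2% | 1.0% | 2.0% |
| 5% | 2.5% | 5.0% |
| 15.4% | 7.7% | 15.4% |

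**4. Effect on hMPV efficacy.** If *s* and *q* are the same in both arms, as 2:1 randomization within China supports for *s*, the factor (1 − *s*) + *s·q* cancels from the rate ratio. A true efficacy of 0% stays 0%, and 30% stays 30%. If sputum detection differed by arm (assumed *q* = 0.3 active, 0.5 placebo) with no true effect:
- *s* = 5%: 1 − (0.95 + 0.015)/(0.95 + 0.025) = 1.0% apparent efficacy.
- *s* = 15.4%: 1 − (0.846 + 0.046)/(0.846 + 0.077) = 3.3%.

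**5. Co-infected RSV cases wrongly kept.** Let *c* be the co-infected fraction of RSV cases and take *s* as the China share of RSV cases. In the worst case, with no China co-infection detected, the kept cases as a share of all cases left in the analysis are *s·c* / [(1 − *s*)(1 − *c*) + *s*].
- *s* = 5%: *c* = 10% gives 0.005/0.905 = 0.6%; *c* = 30% gives 0.015/0.715 = 2.1%.
- *s* = 15.4%: *c* = 10% gives 1.7%; *c* = 30% gives 6.2%.

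The co-infection rates are assumptions.

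**The case against.** A reader might infer from the GeneXpert target list that hMPV and co-infections cannot be detected in China at all. The documents do not support that. China sputum goes to the PN panel, SAP 6.3.3 accepts a nasal or a sputum result, and GeneXpert itself finds influenza A/B co-infection. For the co-infection analyses the sputum route may be well used: LRTD needs three of four symptoms, and every qualifying combination except cough with shortness of breath and wheezing includes coughing up phlegm.

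The assay difference is also prespecified and visible, since SAP 6.3.3 names GeneXpert and 7.7 lists its targets. The outputs are exploratory or sensitivity analyses. China's number is not stated, local cohorts enter only if enrolment began in time, and China's local protocol, which may address this, is not among the documents.

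SAP 6.11 also limits what is still at stake. After termination on 29 March 2023, its list of efficacy endpoints has no hMPV endpoint and no co-infection analysis, and SAP 6.5 makes hMPV at earlier analyses depend on data cleaning.

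All of this reduces the size of the point. What stands is that listing the assay's targets does not tell the analyst to restrict, or the reader to discount, results that pool sites with different detection. SAP 6.5 still says hMPV endpoints will be in the end-of-study analysis, which does not match 6.11.

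**Conclusion.** The point holds as a small gap in ascertainment. hMPV proportions and rates are understated by an illustrative 1-2% (relative) at a 2% China share, 2.5-5% at 5%, and at most about 8-15% at the 15.4% ceiling. These figures assume sputum finds between half and none of China's hMPV cases and that incidence is equal across regions. The co-infection analyses keep some China RSV cases that would be dropped elsewhere, at most about 0.6-6.2% of the remaining cases over the assumed ranges.

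Three stronger readings are not supported:
- That hMPV efficacy is biased. With equal detection by arm it is not, in expectation; a modest difference in sputum yield between arms moves it by only a few points even at the ceiling.
- That 15.4% is China's share. It is the allowance for several countries/territories together.
- That the primary RSV endpoint is affected. RSV is on the China swab assay.

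No change in the co-infection efficacy estimate has been shown either; the defect is an inconsistent definition.

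**What to change.** - **SAP 6.5 (hMPV endpoints):** restrict both cases and follow-up time to participants at sites whose swab assay includes hMPV.
- **SAP 6.3.3 (both co-infection analyses):** run them on participants at full-panel sites, and beside them refit the primary model on the same participants. Otherwise the comparison with the primary result mixes the loss of a region with the removal of co-infections. Showing each analysis with and without China, with a footnote on the assay, is an acceptable alternative.
- **Do not** restrict to ARIs that have a full-panel result. That cannot define follow-up time for participants without an ARI, and in China it selects on sputum production, which occurs after randomization.
- **SAP 6.5 and 6.11:** state whether hMPV endpoints and the co-infection analyses are still to be produced. If not, the changes above are needed only for outputs already generated.

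The cost is one site-level filter, one extra model fit per co-infection analysis and a footnote. The downside is slightly fewer RSV cases in those sensitivity analyses. The primary analysis is untouched.
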